### 8.5.2. Safety Monitoring Rules for Platelet Count Results

Platelet count will be monitored at least every 4 weeks during the Treatment Period. The Investigator should review all platelet count results within 48 hours of receipt. If a patient's platelet count falls to  $100,000/\text{mm}^3$  or less, then the patient's platelet counts should be monitored weekly. In case of platelet reduction to below  $75,000/\text{mm}^3$ , the platelet monitoring rule defined in Stopping rules (Section 8.6.3) should be followed.

In the event of a platelet count  $< 75,000/\text{mm}^3$ , additional laboratory investigations should be conducted (Table 4).

**Table 4: Additional Labs to be Performed in the Event of a Platelet Count  
< 75,000/mm^3**

Peripheral smear (should be performed locally, fixed and sent to central lab for review)
Fibrinogen split products or D-dimer on fresh blood
Citrated sample for platelets
Coagulation panel (prothrombin time [PT]/INR, activated partial thromboplastin time [aPTT])
CBC with reticulocytes and mean platelet volume (MPV)
Serum B12 and folate
Fibrinogen
von Willebrand factor
Total globulins, total IgA, IgG and IgM
Complement: total C3, total C4, Bb, C5a
CRP measured by high sensitivity assay (hsCRP)
Serology for:
hepatitis B virus (HBV), HCV, HIV (if not done for screening)
Rubella
CMV
EBV
Parvo B19
Helicobacter pylori (IgG serum test)
Auto-antibody screen:
Antiphospholipid
Rheumatoid factor
Anti-dsDNA
Anti-thyroid
To Be Performed at Specialty Lab(s):
Antiplatelet antibodies and Anti-PF4 assay
Anti-ASO antibody

Note: The above labs may change as additional data is assessed, and sites will be updated regarding any changes.

## 8.6. Stopping Rules for Liver Chemistry Elevations

For the purposes of the stopping rules, Baseline is defined as:

- Insert a description of what will constitute the Baseline for each of the tests that will be used in the stopping rules. This does not need to be the same definition as will be used in the statistical testing, but it is anticipated that in the same definition will be used wherever possible to avoid confusion
- Monitoring rules for liver chemistry tests – Baseline is defined as average of Screening and Day 1
- Temporary stopping rules for renal function tests – Baseline is defined as average of Screening and Day 1
- Stopping rules for platelets – Baseline is defined as the last non-missing value prior to the first dose

### 8.6.1. Stopping Rules for Liver Chemistry Elevations

In the event of laboratory results meeting the following criteria, **and the event is without an alternative explanation as discussed with the Sponsor Medical Monitor**, dosing of a subject with Study Drug (ION-827359 or placebo) will be stopped permanently; values that are not confirmed due to failure to retest or missing lab values will be presumed confirmed:

1. ALT or AST  $> 8 \times$  ULN, which is confirmed
2. ALT or AST  $> 5 \times$  ULN, which is confirmed and persists for  $\geq 2$  weeks
3. ALT or AST  $> 3 \times$  ULN (or the greater of  $2 \times$  baseline value or  $3 \times$  ULN if the baseline value was  $>$  ULN), which is confirmed **and** total bilirubin  $> 2 \times$  ULN or INR  $> 1.5$
4. ALT or AST  $> 3 \times$  ULN (or the greater of  $2 \times$  baseline value or  $3 \times$  ULN if the baseline value was  $>$  ULN), which is confirmed, **and** the new appearance (i.e., onset coincides with the changes in hepatic enzymes) of fatigue, nausea, vomiting, right upper quadrant pain or tenderness, fever, rash, and/or concomitant eosinophilia ( $>$  ULN)

### 8.6.2. Stopping Rules for Renal Function Test Results / Temporary Stopping Rules for Renal Function Test Results

In the event of laboratory results for either of the following criteria, dosing of a subject with Study Drug (ION-827359 or placebo) will be stopped permanently:

1. Confirmed serum creatinine increase that is both  $\geq 0.5$  mg/dL (26.5  $\mu$ mol/L) and  $\geq 40\%$  above Baseline creatinine values (refer to definition of Baseline in Section 8.6)
2. Proteinuria, dipstick 2 + (confirmed by dipstick retest and then further confirmed by a quantitative total urine protein measurement of  $> 1.0$  g/24 hour)

The follow-up schedule for any events meeting either of these stopping criteria will be determined by the Investigator in consultation with the Sponsor Medical Monitor or designee.

In the event of a persistent elevation that is observed over 2 consecutive weeks, for either of the 2 criteria below, dosing of a patient with Study Drug (ION-827359 or placebo) may be stopped temporarily:

1. Serum creatinine increase that fulfills all of the following criteria:  $\geq 0.5 \text{ mg/dL}$  ( $26.5 \mu\text{mol/L}$ ) and  $\geq 40\%$  above Baseline creatinine values and  $> \text{ULN}$  (refer to definition of Baseline in Section 8.6)
2. Proteinuria, dipstick 2 + (confirmed by dipstick retest and then further confirmed by a quantitative total urine protein measurement of  $> 1.0 \text{ g/24 hour}$ )

The possible dosing re-initiation or follow-up schedule for any events meeting either of these criteria will be determined by the Investigator **in consultation with** the Sponsor Medical Monitor or designee.

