### **8.8. Discontinuation of Study Drug/Treatment**

A subject must permanently discontinue study treatment for any of the following:

- The subject becomes pregnant. Report the pregnancy according to instructions in Section 9.5.4
- The subject withdraws consent
- The subject experiences an AE that necessitates permanent discontinuation of Study Drug
- The subject develops laboratory test abnormalities that meet any of the stopping rules listed in Sections 8.6.1 to 8.6.3
- The subject experiences an AE that necessitates unblinding of the Investigator to the subject's treatment assignment
- Subject has PCR test positive for SARS-CoV-2

The reason for discontinuation of Study Drug must be recorded in the electronic Case Report Form (eCRF) and source documentation.

Patients who discontinue Study Drug will remain in the study and continue protocol required tests and assessments will enter the Post-Treatment Period unless consent is withdrawn. For patients withdrawn for reasons other than withdrawal of consent every effort should be made to complete the early termination of study procedures and observations at the time of withdrawal (see [Appendix A](#)) and ideally within 2 weeks from the last dose of Study Drug. If the patient declines or is unable to participate in the above, the Investigator should clarify what type of follow-up the subject is agreeable to: in person, by phone/mail, through family/friends, via correspondence/communication with other physicians, and/or from review of the medical records. Wherever possible these patients should continue to be followed up via the agreed means to collect information on AEs, concomitant medications and survival status. At the very least, the patient's status at the end of the protocol defined Study Period should be ascertained and documented wherever possible. The agreed means of follow-up will be documented in the patient records and notified to the Sponsor.

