## 1.1 Study Overview

This is a Phase 2a, double blind, randomized, placebo-controlled, dose-ranging study, will be conducted at multiple centers in Europe. Patients with CB associated with COPD will be randomized to ION-827359 or matching placebo administered by oral inhalation once weekly for 13 weeks.

Approximately 180 patients are planned to be enrolled in this study. Patients will be randomized in a 2:2:1:1 ratio to the following 4 treatment groups respectively:

- ION-827359 37.5 mg (1.5 mL) once per week
- ION-827359 75mg (3 mL) once per week
- Placebo (1.5 mL) once per week
- Placebo (3 mL) once per week

There are 3 subset studies:

1. A subset of up to about 24 patients will have PK profile sampling performed after the first and last dose
2. A subset of up to about 60 patients will have low dose inspiratory and expiratory HRCT scans to assess regional lung ventilation performed before and post-treatment
3. A subset of up to about 18 patients will undergo bronchoscopy and BAL for target engagement and inflammatory biomarkers before and post-treatment

A patient may be enrolled in a maximum of 1 subset study.

The study will consist of Screening, Treatment, and Post-Treatment Periods. Please refer to the Schedule of Procedures in protocol Appendix A. The study for an individual patient will generally consist of the following Periods:

- A  $\leq$  4-week Screening Period. The last week of which is the Run-in Period
- A 13-week Treatment Period during which study medication (ION-827359 or placebo) will be administered by nebulization once per week (both in-clinic and at home dosing)
- A 10-week Post-Treatment Period

Patients may be required to attend additional visits for monitoring of AEs or abnormal investigation results. The frequency of additional monitoring will be determined by the Sponsor Medical Monitor in consultation with the Investigator.

Due to a combination of findings in a recently completed chronic toxicology study in non-human primates and the totality of the data collected to date in this and other studies of ENaC inhibition, the study treatment has been terminated on April 29th, 2021, after 60 patients have been randomized and 59 patients have been dosed. All patients who were on treatment at the time of study treatment termination will stop the treatment, continue in the study to complete the early termination visit (Week 14 Day 92) and the 10-week Post-Treatment period.

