#### 2.5.2.3 Central Laboratory Data

The sites will collect the blood and urine samples and send to the central vendor, Medpace. Ionis and Medpace are responsible for the format of the safety laboratory electronic data transfers and the transfer schedule. Central laboratory data results will not be stored in the EDC system. Medpace and Ionis are responsible for the review of the clinical laboratory data. This process involves reviewing the patient and visit identifiers in the central laboratory data results data against the central lab data identifiers collected in the EDC system. Investigator sites have access to the data via lab reports sent directly from the laboratory or through the laboratory's web portal (in which case Investigators only have access to data from their site).

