## 3.2 Demographic and Baseline Characteristics and Patient Disposition

Baseline and demographic variables will be summarized descriptively by treatment group and for each analysis population.

Demographic and baseline characteristics to be presented include age, age category (<18, 18 to 64, ≥65 years), gender, race, ethnicity, height, weight, BMI, , percent predicted DLCO, , baseline spirometry assessments, E-RS scores, CAT scores, SGRQ scores, sputum mucins, FRC and RV.

For race summary, if multiple races are recorded in database, 'Multiple Race' will be used in the summary table but details records in the listing.

A separate table will be created for the targeted medical history and smoking history, and will include duration since diagnosis of COPD, COPD exacerbations that required hospitalization in the last year (yes/no), number of hospitalizations for COPD exacerbations in the last year, COPD exacerbations that required oral corticosteroids and/or antibiotic in the last year (yes/no), number of COPD exacerbations in the last year that required oral corticosteroids and/or antibiotics, diagnosis with asthma (yes/no), diagnosis with coronary artery disease (yes/no), diagnosis of congestive heart failure (yes/no), ever used tobacco cigarettes (yes/no), number of packs tobacco per day and number of years smoking.

The duration since diagnosis of COPD will be calculated as the difference between informed consent date and COPD diagnosis date plus 1 day then divided by 365.25. The partial COPD dates will be imputed using the following rules:

- If both month and day are missing then assign July 1st
- If only day is missing then assign 15th

Other medical history data will be provided in the data listing and summarized using MedDRA SOC and preferred term.

Subject enrollment and disposition will be summarized by treatment group. The summary will include: the number of subjects screened, the number of screen failures, the reason for screen failure, the number of subjects randomized, the number and percentage of subjects dosed, the number and percentage of subjects in each analysis population, the number and percentage of subjects in each subgroup, the number and percentage of subjects completing treatment, the primary reason for terminating treatment, the number of subjects completing post-treatment follow-up, and the primary reason for terminating post-treatment follow-up. The percentages will be calculated based on the number of patients randomized.

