### **3.4.3      Laboratory Measurements**

The list of safety lab analytes collected throughout the study is provided in protocol Appendix B.

All lab data collected will be presented in subject listings.

Results from chemistry, hematology, complements, and coagulation panels as well as the change and percent change from baseline will be summarized by treatment group and study visit using descriptive statistics.

For ALT and AST, the number and percent of subjects falling in each of the following categories based on the confirmed results will be tabulated by treatment group

- ALT/AST > 3 x ULN, which is confirmed
- ALT/AST > 5 x ULN, which is confirmed

For platelet, the number and percentage of subjects falling in each of the following categories based on the confirmed results will be tabulated by treatment group for 100,000/mm^3 to <140,000/mm^3 and <100,000/mm^3.

A confirmed value is based on a consecutive lab value within 7 days. If that value is in the same or worse category the initial value is confirmed. If the consecutive value is in a better category, then the initial value is confirmed using the consecutive value category. If there is no retest within 7 days, then the initial value is presumed confirmed. If there are multiple results on the same day, then the worst value will be utilized in the analysis.

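### Protocol 8.6.2 gives the creatinine stopping threshold as 0.5 mg/dL (26.5 µmol/L), but 0.5 mg/dL is 44.2 µmol/L, and nothing says which figure governs

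*Combined protocol and SAP*

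**What the plan says.** Protocol Section 8.6.2 has two creatinine criteria.

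- **Permanent stop (mandatory).** "Confirmed serum creatinine increase that is both $\geq 0.5$ mg/dL (26.5 $\mu$ mol/L"), and at least 40% "above Baseline creatinine values".
- **Temporary stop (optional).** "Serum creatinine increase that fulfills all of the following criteria": the same absolute pair, the same 40% condition and a value above ULN, with the elevation persisting over two consecutive weeks.

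Both criteria refer to Section 8.6 for Baseline. That section gives the average of Screening and Day 1 and lists it under the temporary renal rules. Section 8.5 adds that an initial value reaching a stopping rule bars further dosing until the retest is available. Section 8.8 makes meeting the renal rule a reason for permanent discontinuation.

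On laboratory handling, SAP 2.5.2.3 says "The sites will collect the blood and urine samples and send to the central vendor"; it states no reporting unit. Appendix D grades creatinine adverse events in mg/dL only, by absolute level, with the mild grade starting at 1.5 mg/dL.

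SAP 1.1 records that "the study treatment has been terminated on April 29th, 2021, after 60 patients have been randomized and 59 patients have been dosed".

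**The concern.** A figure in brackets after a threshold is read as the same quantity in other units. Here it is a different and lower quantity. Anyone working from a µmol/L report would apply a stricter rule than someone working from mg/dL, and both would be following the printed text. Because the permanent rule is mandatory, the discrepancy can reverse a discontinuation decision, and through Section 8.5 it can also decide whether a dose is held pending a retest.

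The stake is now retrospective. Dosing has ended. SAP 3.4.3 tabulates thresholds for ALT/AST and platelets only, so no planned threshold table changes. But safety and tolerability is a secondary objective, and the disposition summary in SAP 3.2 will show "the primary reason for terminating treatment". A reader of the report cannot tell which renal threshold produced, or failed to produce, a stop.

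**Working it through.** **Inputs**

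- Printed pair: 0.5 mg/dL and 26.5 µmol/L (protocol 8.6.2, twice).
- Relative condition: at least 40% above Baseline (protocol 8.6.2).
- Conversion: not in the documents. It follows from the molar mass of creatinine, C4H7N3O: 4 × 12.011 + 7 × 1.008 + 3 × 14.007 + 15.999 = 113.12 g/mol. Then 1 mg/dL = 10,000 / 113.12 = 88.4 µmol/L.

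**Step 1. Try to reproduce the printed equivalent**

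- 0.5 × 88.4 = 44.2 µmol/L, not 26.5.
- 26.5 / 88.4 = 0.30 mg/dL, not 0.5.
- Ratio: 44.2 / 26.5 = 1.67.

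Rounding does not explain the gap. With the molar mass varied from 113.0 to 113.2, 0.5 mg/dL stays between 44.17 and 44.25 µmol/L. For the printed pair to agree, the molar mass would have to be 0.5 × 10,000 / 26.5 = 188.7 g/mol.

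**Step 2. Where the permanent rule gives two answers**

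The rise needed to stop is the larger of the absolute threshold and 0.40 × baseline. The readings therefore conflict for a confirmed rise that is

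- at least max(26.5, 0.40 × baseline), and
- below 44.2 µmol/L.

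The band has its full width, 44.2 − 26.5 = 17.7 µmol/L, up to a baseline of 26.5 / 0.40 = 66.3 µmol/L. It closes at 44.2 / 0.40 = 110.5 µmol/L, which is 0.5 / 0.40 = 1.25 mg/dL. From there upward the 40% condition decides and the two readings agree.

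| Baseline (µmol/L) | Disputed rise (µmol/L) | Width (µmol/L) |
|---|---|---|
| 60 | 26.5 to <44.2 | 17.7 |
| 70 | 28.0 to <44.2 | 16.2 |
| 80 | 32.0 to <44.2 | 12.2 |
| 90 | 36.0 to <44.2 | 8.2 |
| 100 | 40.0 to <44.2 | 4.2 |
| 110 | 44.0 to <44.2 | 0.2 |

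As creatinine levels in mg/dL, the disputed range is 1.12 to <1.30 at baseline 0.8 (0.8 + 0.32 to 0.8 + 0.5) and 1.40 to <1.50 at baseline 1.0 (1.0 + 0.40 to 1.0 + 0.5).

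**Step 3. Worked case**

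A confirmed rise from 0.8 to 1.2 mg/dL is 0.4 / 0.8 = +50%, and 0.4 × 88.4 = 35.4 µmol/L.

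- By the µmol/L figure: 35.4 ≥ 26.5 and 50% ≥ 40%, so dosing stops permanently.
- By the mg/dL figure: 0.4 < 0.5, so dosing continues.

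**Step 4. Does Appendix D settle it?**

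No. It grades levels, not increases. For any baseline up to 1.0 mg/dL, a rise below 0.5 gives a level below 1.5 mg/dL, so the whole disputed range lies below the mild grade.

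These bands do not carry over to the temporary rule. It has the same unit error, but its ULN and persistence conditions narrow the range, and the stop is discretionary.

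**The case against.** The strongest reply is that the intended rule is clear enough. In both criteria mg/dL comes first and µmol/L follows in brackets, and Appendix D uses mg/dL only, so the natural reading is a 0.5 mg/dL rule with a faulty conversion. That is a reasonable inference, but the text does not say it. The faulty figure is the more cautious of the two, and a reader whose laboratory report is in µmol/L has no reason to distrust it.

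A second reply is that little now depends on the rule. Treatment has stopped, the efficacy analyses are descriptive, no table uses a creatinine threshold, and no document reports a renal stop or a misapplied rule. All of this stands, and it limits the consequence to how past decisions were made and reported. With one central laboratory, a difference between sites is possible but not shown.

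Third, patients in the disputed range were not unwatched. Section 8.5 requires confirmation of results, Section 6.1.3 provides for ongoing Medical Monitor review, and Section 8.8 allows discontinuation for an adverse event whatever the numeric rule says. These safeguards reduce the safety effect but do not choose between the figures.

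Finally, a recheck needs a stated baseline. The SAP's general baseline for creatinine is the last value before the first dose, whereas 8.6.2 points to the Section 8.6 average. This is a fair practical point, and the fix below takes it up.

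**Conclusion.** The threshold is wrong as written. The printed figures differ by a factor of 1.67 (44.2 against 26.5 µmol/L), and under the permanent rule they can give opposite decisions at any baseline below 110.5 µmol/L (1.25 mg/dL). The disputed range is at most 17.7 µmol/L wide and shrinks to nothing at that baseline.

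The conclusion rests only on the printed figures and the molar mass of creatinine. It makes no claim about which figure was intended, how often a confirmed rise fell in the range, or whether any patient was managed wrongly; the documents give no data on these. Because this is a mandatory safety threshold, it is more than a typographical matter, although the end of dosing confines the remaining effect to the 59 patients already treated.

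**What to change.** 1. State one threshold with its correct equivalent in both criteria of 8.6.2, either 0.5 mg/dL (44.2 µmol/L) or 0.3 mg/dL (26.5 µmol/L), and name the governing unit. The sponsor must say which was intended. With dosing over, a dated clarification carried into the study report would serve.
2. Recheck the on-treatment creatinine results and any renal discontinuations of the 59 dosed patients against the declared threshold, using the Section 8.6 baseline (average of Screening and Day 1), not the SAP's general baseline.
3. Report how many confirmed rises fell between the two printed figures, even if none, and what was done in each case.

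The cost is small: one figure corrected in two places and a check of data already held. Appendix A schedules five post-baseline pre-dose chemistry panels (Days 15, 29, 43, 57 and 85), so there are at most 59 × 5 = 295 scheduled results plus retests, and fewer in practice because treatment stopped early. The averaged baselines have to be derived for this check. The sources are in place: SAP 3.4.3 says "All lab data collected will be presented in subject listings", and protocol 8.8 says "The reason for discontinuation of Study Drug must be recorded in the electronic Case Report Form". No new tests or patients are needed.

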## 8.5. Safety Monitoring Rules

Please refer also to the ‘Guidance for Investigator’ section of the Investigator’s Brochure.

For the purposes of Safety Monitoring Baseline is defined as:

- Monitoring Rules for Liver Chemistry Tests – Baseline is defined as the average of Screening and Day 1

In addition to the standard monitoring of clinical safety parameters, the following guidelines are provided for the monitoring of selected parameters chosen based on preclinical and clinical observations.

Confirmation Guidance: At any time during the study (Treatment or Post-Treatment Periods), the initial clinical laboratory results meeting the safety monitoring criteria presented below **must be confirmed** by performing measurements (ideally in the same laboratory that performed the initial measurement) on new specimens. All new specimen collections should take place as soon as possible (ideally within 3 days of the initial collection). For stopping rules, if the initial laboratory result is observed during the Treatment Period, the results from the retest **must be available** prior to administering the next dose of Study Drug (ION-827359 or placebo).

Re-dosing Guidance: Patients with initial laboratory test values that reach a stopping rule must not be re-dosed until the re-test results are available. In general, patients who do not meet the stopping rules based upon retest may continue dosing. However, the Investigator and the Sponsor Medical Monitor (or appropriately qualified designee) should confer as to whether additional close monitoring of the subject is appropriate. If any of the stopping criteria described below (refer to Sections 8.6.1 to 8.6.4 are met, the subject will be permanently discontinued from further treatment with Study Drug (ION-827359 or placebo), evaluated fully as outlined below and in consultation with the Sponsor Medical Monitor or appropriately qualified designee, and will be followed up in accordance with Section 8.8 of the protocol.

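### Section 8.6.2 contradicts itself: its optional temporary renal hold covers only results that already require a permanent stop

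*Combined protocol and SAP*

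**What the plan says.** Section 8.6.2 of the protocol contains two lists under one heading, whose two titles are joined by a slash.

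For the first list, "dosing of a subject with Study Drug (ION-827359 or placebo) will be stopped permanently". The triggers are a confirmed serum creatinine increase of at least 0.5 mg/dL and at least 40% above Baseline, or "Proteinuria, dipstick 2 + (confirmed by dipstick retest and then further confirmed by a quantitative total urine protein measurement of" more than 1.0 g/24 hour.

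The second list opens with a persistence condition, "In the event of a persistent elevation that is observed over 2 consecutive weeks", and continues: "for either of the 2 criteria below, dosing of a patient with Study Drug (ION-827359 or placebo) may be stopped temporarily". Its triggers are the same creatinine thresholds with the further condition that the value exceeds ULN, or proteinuria in the same words as before. It closes with: "The possible dosing re-initiation or follow-up schedule for any events meeting either of these criteria will be determined by the Investigator", acting together with the Sponsor Medical Monitor or a designee.

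Both creatinine criteria carry the pointer "refer to definition of Baseline in Section 8.6". Section 8.6 has one renal Baseline bullet (the average of Screening and Day 1). It is labelled as belonging to the temporary rules. The same section still contains a template instruction telling the author to insert a description of Baseline.

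Two other sections bear on the action. The re-dosing guidance in Section 8.5 requires permanent discontinuation when any stopping criterion in 8.6.1 to 8.6.4 is met. Section 8.8 makes meeting any stopping rule in 8.6.1 to 8.6.3 a reason for mandatory permanent discontinuation.

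**The concern.** A mandatory stopping rule should lead to one action for a given result. Here the same confirmed proteinuria calls for a permanent stop in one paragraph and an optional, reversible hold in the next. For creatinine, the extra conditions in the second list make the finding more marked and longer-lasting, yet the action attached to it is weaker. Section 8.6.2 does not say which list takes precedence or that the two serve different situations.

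At stake is consistent handling of renal safety findings. Section 2.5 names renal sodium wasting and hyperkalemia among the possible consequences of lost ENaC function, and Section 5.2 screens patients on creatinine, estimated GFR and urine protein. A reader who acts on the second list could propose a restart for a patient whom the first list has already stopped for good.

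**Working it through.** The plan gives no figure to reproduce here. The check sets the two lists side by side and asks whether any result can meet the second without meeting the first.

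| Element | First list | Second list |
|---|---|---|
| Action | Permanent, mandatory | Temporary, optional |
| Duration | None stated | Elevation over 2 consecutive weeks |
| Creatinine | Rise of at least 0.5 mg/dL and at least 40% above Baseline, confirmed | Same thresholds, plus above ULN |
| Proteinuria | 2+, dipstick retest, more than 1.0 g/24 hour | Identical |
| Baseline for creatinine | Section 8.6 | Section 8.6 |
| Afterwards | Follow-up schedule | Possible re-initiation or follow-up |

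**Proteinuria.** Both lists require the same dipstick result and the same two confirmations. The second adds only persistence. Any result that meets the second list meets the first.

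**Creatinine.** Write B for Baseline and v for the measured value.

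- Permanent: v − B ≥ 0.5 mg/dL and v ≥ 1.4 × B, confirmed.
- Temporary: v − B ≥ 0.5 mg/dL and v ≥ 1.4 × B and v > ULN, over 2 consecutive weeks.

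The second list omits the word confirmed. However, Section 8.5 treats confirmation as a measurement on a new specimen, and an elevation seen over 2 consecutive weeks needs at least a second specimen. The retest interval in 8.5 is given as an ideal, so a later specimen still counts. The temporary criterion is therefore nested in the permanent one.

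Two illustrations follow. Baseline, ULN and measured values are assumed, since the documents give none.

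- B = 1.0, ULN = 1.3, two successive weekly values of 1.6 mg/dL. Rise 1.6 − 1.0 = 0.6; 0.6/1.0 = 60%; above ULN. Both rules are met, with conflicting actions.
- B = 0.6, ULN = 1.2, two values of 1.15 mg/dL. Rise 1.15 − 0.6 = 0.55; 0.55/0.6 = 92%; not above ULN. Only the permanent rule is met.

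The patient still below ULN has no route to a restart, while the patient above it is offered one.

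**Count.** 2 of 2 temporary criteria lie wholly inside the permanent rule. The reverse does not hold, because the permanent rule also catches creatinine rises that stay at or below ULN and findings that do not last 2 weeks.

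**Other sections.** The ranges cited in 8.5 and 8.8 take in the whole of 8.6.2 without separating its two lists. Read literally, even the temporary criteria lead to permanent discontinuation there. Those sections favour the permanent stop but leave the restart sentence in place.

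**Is it deliberate discretion?** Where the protocol wants an exception, it writes one into the rule. Section 8.6.1 excuses events with an alternative explanation, and 8.6.4 excuses a potassium rise with a clear etiology. The permanent renal rule has no such clause.

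**The case against.** The strongest reply is that precedence is already settled. The permanent rule comes first within 8.6.2, and 8.5 and 8.8 both require permanent discontinuation. Misapplication would need a reader to miss all three and the Sponsor Medical Monitor to agree, since the restart sentence requires that consultation. A reader might infer that a site could restart a patient on its own decision. The text does not support that. This reply stands as a limit on the harm, but it does not remove the contradictory wording.

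A second reply is that the lists are not the same, because the second adds ULN and persistence. That is true for creatinine, and it is why the criteria are nested and not identical. It does not help the text, since the additions only narrow the trigger.

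A third reply concerns intent. The slash in the heading and the leftover instruction in 8.6 suggest that two template options were both kept, but this is inference. The renal Baseline bullet is labelled temporary, so the sponsor may even have meant to keep the temporary rule. The documents do not settle which. A reader might also infer from that label that the permanent rule has no Baseline. It does, because its criterion points to Section 8.6, which gives only one renal definition.

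Finally, a reader might suspect that a patient who met the rule was dosed again. Nothing in the documents says so.

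**Conclusion.** Section 8.6.2 is internally inconsistent as written. The temporary block has no case of its own to govern, and it attaches a weaker, optional action to the more persistent finding. This rests on reading the text, with one assumption: that a creatinine elevation present over 2 consecutive weeks counts as confirmed.

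The severity is minor. The consequence is a limited risk that like results are handled differently. SAP Section 1.1 records that treatment was terminated on 29 April 2021 after 59 patients had been dosed, so a correction cannot change dosing in this trial. No frequency of renal events is given, so none is estimated. The rule enters no endpoint definition or planned efficacy analysis.

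**What to change.** Delete the second list and its re-initiation sentence from Section 8.6.2. The interim protection is already in Section 8.5: "Patients with initial laboratory test values that reach a stopping rule must not be re-dosed until the re-test results are available". Deletion is the conservative choice and agrees with 8.5 and 8.8.

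If the sponsor wants a temporary hold, set it at a threshold below the permanent rule and exclude it from the permanent-stop references in 8.5 and 8.8. Otherwise those sections would override it.

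In Section 8.6, relabel the renal Baseline bullet so that it covers the permanent rule, and remove the template instruction.

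The cost is wording only. For this trial, the sponsor could also list any dosed patient who met 8.6.2, with the action taken. The SAP already plans laboratory listings (3.4.3), dose interruptions (3.4.1) and reasons for terminating treatment (3.2). For proteinuria, such a listing depends on whether the confirming 24-hour urine protein was captured, because it is not among the Appendix B analytes.
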